15.3. Sample Size Considerations

No formal sample size calculation has been made. The sample size has been selected to provide adequate information on safety, tolerability, PK, and PD following single and multiple doses of EP547.

15.4. Safety Analysis

The Safety Population will be used for the summaries of the safety data according to the treatment received.

The safety and tolerability of EP547 will be assessed by comparing the frequency and severity of AEs as well as treatment discontinuations due to AEs. AEs will be coded using the Medical Dictionary for Regulatory Activities (MedDRA) by System Organ Class and preferred term. The World Health Organization (WHO) DRUG Dictionary will be used to categorize verbatim descriptions of non-study medications into the Anatomic Therapeutic Chemistry (ATC) classification system. Changes in vital signs, body weight, physical examinations, standard 12-lead ECGs, and laboratory evaluations will be compared across dose levels, when applicable, and to placebo.

Cardiodynamic analysis of the data from Holter monitoring will be conducted separately.

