15.2. Outcome Measures

15.2.1. Primary Safety Outcome Measures

Primary safety outcome measures include:

- AEs
- Clinical laboratory assessments
- Vital signs and body weight
- Standard 12-lead ECGs
- Physical examinations

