### 3.7 Treatment Groups/Treatment Sequence

#### 3.7.1 Baseline Characteristic, Demography, Safety and PD outputs

For listings, all segment data will be presented together in one listing as per segment and dose level (available) with the following treatment group labels:

- Group 1: SAD HS/ EP547 25 mg
- Group 2: SAD HS/ EP547 75 mg
- Group 3: SAD HS/ EP547 225 mg
- Group 4: SAD HS/ EP547 450 mg
- Group 5: SAD HS/ EP547 TBD mg
- Group 6: MAD HS/ EP547 25 mg QD
- Group 7: MAD HS/ EP547 75 mg QD
- Group 8: MAD HS/ EP547 TBD mg QD
- Group 9: SD CP/ EP547 TBD mg
- Group 10: SD UP/ EP547 TBD mg
- Group 11: MAD CP/ EP547 TBD mg QD
- Group 12: MAD CP/ EP547 TBD mg QD (optional)
- Group 13: MAD UP/ EP547 TBD mg QD
- Group 14: MAD UP/ EP547 TBD mg QD (optional)

For summary, separate tables will be provided for each segment (SAD-HS, MAD-HS, SD-CP/SD-UP, MAD-CP/MAD-UP) with the following treatment group labels:

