### **13. SAFETY**

Safety endpoints will be analyzed using the Safety Population. Safety endpoints will be summarized descriptively as described in section 3.1.

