### **13.5 Physical Examinations**

By-participant data listings will be created for all physical examination parameters and all time points.

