14.3.4.3.2d	Urinalysis Results - Out of Normal Range Values – MAD-CP/MAD-UP	Safety		×
14.3.4.3.2e	Urinalysis Results - Out of Normal Range Values – FE-HS	Safety		
14.3.4.3.3a	Urinalysis Results - Normal/Abnormal Shift Table – SAD-HS	Safety	×	×
14.3.4.3.3b	Urinalysis Results - Normal/Abnormal Shift Table – MAD-HS	Safety	×	×
14.3.4.3.3c	Urinalysis Results - Normal/Abnormal Shift Table – SD-CP/SD-UP	Safety		×
14.3.4.3.3d	Urinalysis Results - Normal/Abnormal Shift Table – MAD-CP/MAD-UP	Safety		×

Table Number	Table Title	Population	Interim	Final
14.3.4.3.3e	Urinalysis Results - Normal/Abnormal Shift Table – FE-HS	Safety		
14.3.5	Other Safety			
14.3.5.1a	Vital Signs - Values and Change from Baseline – SAD-HS	Safety	×	×
14.3.5.1b	Vital Signs - Values and Change from Baseline – MAD-HS	Safety	×	×
14.3.5.1c	Vital Signs - Values and Change from Baseline – SD-CP/SD-UP	Safety		×
14.3.5.1d	Vital Signs - Values and Change from Baseline – MAD-CP/MAD-UP	Safety		×
14.3.5.1e	Vital Signs - Values and Change from Baseline – FE-HS	Safety		
14.3.5.2a	12-Lead ECG Results - Change of 12-Lead ECG Values – SAD-HS	Safety	×	×
14.3.5.2b	12-Lead ECG Results - Change of 12-Lead ECG Values – MAD-HS	Safety	×	×
14.3.5.2c	12-Lead ECG Results - Change of 12-Lead ECG Values – SD-CP/SD-UP	Safety		×
14.3.5.2d	12-Lead ECG Results - Change of 12-Lead ECG Values – MAD-CP/MAD-UP	Safety		×
14.3.5.2e	12-Lead ECG Results - Change of 12-Lead ECG Values – FE-HS	Safety		
14.3.5.3a	12-Lead ECG Results - Normal/Abnormal Shift Table – SAD-HS	Safety	×	×
14.3.5.3b	12-Lead ECG Results - Normal/Abnormal Shift Table – MAD-HS	Safety	×	×
14.3.5.3c	12-Lead ECG Results - Normal/Abnormal Shift Table – SD-CP/SD-UP	Safety		×
14.3.5.3d	12-Lead ECG Results - Normal/Abnormal Shift Table – MAD-CP/MAD-UP	Safety		×
14.3.5.3e	12-Lead ECG Results - Normal/Abnormal Shift Table – FE-HS	Safety		
14.3.5.4c	Hemodialysis – SD-UP	Safety		×
14.3.5.4d	Hemodialysis – MAD-UP	Safety		×

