16.2.6.17e	[REDACTED]	Enrolled		
16.2.7	Adverse Events			
16.2.7.1	Adverse Events	Enrolled	X	X
16.2.7.1e	Adverse Events – FE-HS	Enrolled		
16.2.7.2	Serious Adverse Events	Enrolled	X	X
16.2.7.2e	Serious Adverse Events – FE-HS	Enrolled		
16.2.7.3	Drug-Related Adverse Events	Enrolled	X	X
16.2.7.3e	Drug-Related Adverse Events – FE-HS	Enrolled		
16.2.7.4	Adverse Events Leading to Study Drug Discontinuation	Enrolled	X	X
16.2.7.4e	Adverse Events Leading to Study Drug Discontinuation – FE-HS	Enrolled		
16.2.7.5	Adverse Events with Outcome of Death	Enrolled	X	X
16.2.7.5e	Adverse Events with Outcome of Death – FE-HS	Enrolled		
16.2.8	Laboratory Parameters			
16.2.8.1	Hematology Results	Enrolled	X	X
16.2.8.1e	Hematology Results – FE-HS	Enrolled		
16.2.8.2	Chemistry Results	Enrolled	X	X
16.2.8.2e	Chemistry Results – FE-HS	Enrolled		
16.2.8.3	Urinalysis Results	Enrolled	X	X
16.2.8.3e	Urinalysis Results – FE-HS	Enrolled		

Listing Number	Listing Title	Population	Interim	Final
16.2.9	Other Safety			
16.2.9.1	Vital Signs	Enrolled	X	X
16.2.9.1e	Vital Signs – FE-HS	Enrolled		
16.2.9.2	12-Lead Electrocardiogram	Enrolled	X	X
16.2.9.2e	12-Lead Electrocardiogram – FE-HS	Enrolled		
16.2.9.3	Physical Examination	Enrolled	X	X
16.2.9.3e	Physical Examination – FE-HS	Enrolled		
16.2.9.4	Hemodialysis	Enrolled	X	X
16.2.9.5	Holter Monitoring	Enrolled	X	X
16.2.10	Prior & Concomitant Medication			
16.2.10	Prior and Concomitant Medication	Enrolled	X	X
16.2.10e	Prior and Concomitant Medication – FE-HS	Enrolled		
16.2.11	Comments			
16.2.11	Comment Log	Enrolled	X	X

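### No planned output makes the comparison of physical examination changes across doses and with placebo that Protocol 15.4 promises; the SAP only lists them

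*Protocol*

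**What the plan says.** Protocol 15.2.1 names five primary safety outcome measures, and the last of them is "Physical examinations". SAP 2.3.1 repeats the list as primary endpoints. Protocol 15.4 states the analysis: changes in vital signs, body weight, "physical examinations, standard 12-lead ECGs, and laboratory evaluations will be compared across dose levels, when applicable, and to placebo".

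The opening of SAP 13 makes a general promise: "Safety endpoints will be summarized descriptively as described in section 3.1". SAP 3.1 then describes summaries by treatment group and nominal visit, with counts and percentages for categorical data.

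SAP 13.5, which deals with this endpoint, consists of one sentence: "By-participant data listings will be created for all physical examination parameters and all time points". The only outputs indexed for it are listing 16.2.9.3 and its food-effect counterpart 16.2.9.3e, "Physical Examination – FE-HS", both on the Enrolled Population. SAP 18 has no physical examination table. SAP 15 records changes to the planned analysis as not applicable.

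For listings, SAP 3.7.1 says that "all segment data will be presented together in one listing as per segment and dose level (available) with the following treatment group labels". The 14 labels that follow each name a segment and EP547. None names placebo. The summary-table labels in the same section do include placebo columns.

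**The concern.** The protocol commits to a comparison on a primary outcome, and the SAP does not carry it into any output. SAP 13.5 also conflicts with the general sentence that opens SAP 13, so a programmer working from the table index would produce no summary. Because SAP 15 declares no change, a reader of the study report would not learn that the comparison had been dropped.

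What is at stake is a by-arm view of examination findings that were not reported as adverse events. Laboratory and ECG results get exactly that view, through normal/abnormal categories and shift tables. Physical examinations do not.

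**Working it through.** The plan states no figure for this point. The check is a count of planned outputs and a reading of the sections against each other.

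**Summary tables per primary safety outcome (SAP 18).** The index uses five table groups: SAD-HS, MAD-HS, SD-CP/SD-UP, MAD-CP/MAD-UP and FE-HS.

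| Outcome | Table types × groups | Tables |
|---|---|---|
| Adverse events (14.3.3.1 to 14.3.3.6) | 6 × 5 | 30 |
| Laboratory (14.3.4.1.1 to 14.3.4.3.3) | 9 × 5 | 45 |
| Vital signs, including body weight (14.3.5.1) | 1 × 5 | 5 |
| Standard 12-lead ECG (14.3.5.2, 14.3.5.3) | 2 × 5 | 10 |
| Physical examinations | none | 0 |

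Total: 30 + 45 + 5 + 10 + 0 = 90. The ECG set already contains the kind of table that is missing here, for example "12-Lead ECG Results - Normal/Abnormal Shift Table – SAD-HS".

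**Where the promised comparison applies.**

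- SAD-HS: five or six dose levels of 6 EP547 and 2 placebo. At five levels, 5 × 2 = 10 of 5 × 8 = 40 subjects are on placebo. Both comparisons apply.
- MAD-HS: three dose levels. 3 × 2 = 6 of 3 × 8 = 24 are on placebo. Both comparisons apply.
- MAD-CP and MAD-UP: 3:1 allocation, so 2 of 8 per level. The placebo comparison applies; the comparison across doses applies only if a second level is opened.
- SD-CP and SD-UP: one dose level each, no placebo. Neither applies.
- FE-HS: one dose, no placebo. Neither applies.

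So the gap concerns four of the seven segments. In the index's layout these are three of the five table groups, because MAD-CP and MAD-UP share tables.

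The qualifier about applicability in Protocol 15.4 attaches to the comparison across dose levels. It does not release the placebo comparison, and SAD-HS and MAD-HS plainly have several dose levels.

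**Which examinations exist (Protocol 11.7, Appendices A and B).**

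- Single-dose segments: complete at Screening, abbreviated on Day -1, complete on Day 8.
- Multiple-dose segments: complete at Screening, abbreviated on Days -1 and 14, complete on Day 21.
- Early termination: complete in all segments.

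The abbreviated examination covers HEENT, cardiovascular, chest/lung, abdomen and extremities. It omits general appearance, skin, musculoskeletal, thyroid/endocrine and neurologic. For those systems the last scheduled predose value is from Screening, and Day 14 has no scheduled value.

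**The case against.** The strongest reply is that nothing is lost. Protocol 15.8 calls comparisons with placebo qualitative, Protocol 15.4 promises no particular table, and each healthy-subject dose level has only 8 subjects. The arm can be recovered from the randomization and study drug administration listings (16.2.5.1 and 16.2.5.2), and SAP 3.1 says listings are sorted by treatment group. Examination findings recorded as adverse events enter the treatment-emergent tables, which have placebo columns. Body weight is tabulated with vital signs.

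Most of this stands, and it limits the point. A reader might infer that the trial cannot compare examinations between arms. The documents do not support that: the data are collected and the arm is recoverable. What is absent is any planned output that makes the comparison. A qualitative comparison needs no test, but it still needs a display by arm. The adverse event tables do not provide it for findings that were never recorded as adverse events, and the SAP does not treat adverse event capture as enough for laboratory or ECG results.

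A reader might also infer from SAP 3.7.1 that the quarter of subjects on placebo have no place in the listings, or sit under an EP547 dose. The text does not settle this. The labels can be read as cohort names, in the way Protocol 7.1.1 describes each group as EP547 or matching placebo, and many doses are still placeholders. The labels govern all baseline, safety and PD listings, so this is an ambiguity to clear up and not a defect peculiar to physical examinations.

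Review by the Safety Review Team is not a substitute. Under Protocol 7.1 it uses data through the end of Visit 2, and every scheduled examination up to then is predose.

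**Conclusion.** The point holds in a limited form. Protocol 15.4 specifies a comparison for a primary safety outcome, and none of the planned outputs delivers it in SAD-HS, MAD-HS, MAD-CP or MAD-UP. Physical examination is the only one of the five primary safety outcomes with no summary table: 0, against 90 for the other four. The mismatch is both between protocol and SAP and within the SAP, and SAP 15 does not disclose it.

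It would be too much to say that all five table groups lack a promised comparison. SD-CP, SD-UP and FE-HS have one dose level each and no placebo, so the commitment has nothing to act on there.

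The consequence is modest: findings not reported as adverse events go without a by-arm display, though it could be rebuilt by merging listings. The conclusion rests on the table and listing indexes being complete for this endpoint. The documents do not show how the eCRF codes examination findings, so the form of the summary has to follow what it records.

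**What to change.** Add to SAP 13.5 and the table index, for SAD-HS, MAD-HS, MAD-CP and MAD-UP, a descriptive summary or shift table of physical examination findings by body system, with columns for each dose level and pooled placebo. Use the categories the eCRF records; if they include normal and abnormal with clinical significance, the ECG shift table in SAP 13.4 is a ready model. Use the Safety Population by treatment received, as Protocol 15.4 requires for safety summaries.

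- **Baseline:** for each body system, the last predose examination that assessed it. That is normally Day -1 for the systems in the abbreviated examination and Screening for the rest. A single rule based on Day -1 would leave several systems without a baseline.
- **Follow-up:** Day 8 for the single-dose segment and Day 21 for the multiple-dose segments. Use Day 14 only for the systems in the abbreviated examination.
- **Listings:** make the SAP 3.7.1 labels show placebo explicitly.

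If listing only is what is intended, declare it in SAP 15 and align Protocol 15.4 and the opening of SAP 13.

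The cost is one extra table shell per placebo-controlled segment, or three tables if MAD-CP and MAD-UP share one as elsewhere in the index. No new examination is needed.

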15.5. Pharmacokinetic Analysis

Depending on the segment, different PK parameters for plasma EP547 concentrations and metabolites (as applicable) will be calculated. The actual sampling times will be used in the PK parameter calculations. The PK parameters to be determined or calculated using NCA from the

plasma concentration data for EP547 include, but are not limited to, the parameters as listed below:

- SAD segments: C_{max} , t_{max} , k_{el} , $t_{1/2}$, AUC_{∞} , AUC_t , $\%AUC_{extra}$, CL/F , and V_z/F
- MAD segments: C_{max} , C_{trough} , t_{max} , k_{el} , $t_{1/2}$, AUC_{τ} (as appropriate), AUC_t , CL/F , V_z/F , and R_{ss}

To assess dose proportionality, a power model will be applied to the PK parameters, C_{trough} , C_{max} , AUC_t , AUC_{∞} , and AUC_{τ} (as appropriate). For the MAD segment parameter AUC_t , visit day will be added as a fixed effect in the mixed model. The details of the analysis will be described in the SAP.

The following PK parameters for urine EP547 concentrations and metabolites (as applicable) will be calculated using NCA for the SAD-HS segment: A_e , F_e , CLr .

Skin EP547 and metabolites (as applicable) concentrations will be summarized.

For PK analyses, only the EP547 treatment groups will be statistically analyzed. Plasma, urine, and skin concentrations of EP547 will be listed and summarized by nominal timepoint (as applicable) and treatment group. The PK parameters will be listed and summarized by treatment.

[REDACTED]

15.7. Subgroup Analyses

Given the small sample size, no formal subgroup analyses are planned for this study.

15.8. Multiple Comparison/Multiplicity

This is the first study to evaluate EP547. Statistical methodologies adjusting for multiple comparisons do not apply because comparisons to placebo in this Phase 1 study are qualitative rather than quantitative.

15.9. Planned Interim Analysis

An interim analysis may be conducted during the study at a time the Sponsor deems appropriate. The interim analysis would be administrative in nature to address business needs.

Additional details about the interim analysis, if applicable, will be provided in the SAP, which is to be finalized before the database lock and unblinding of the study data, as applicable, for the interim analysis. The SAP will be amended if emerging data from the completed interim analysis leads to substantial change in the study protocol that has significant impact on the statistical analyses.

16. QUALITY CONTROL AND DATA MANAGEMENT

16.1. Data Quality Assurance

The following measures will be implemented to ensure accuracy, consistency, completeness, and reliability of data:

- Investigator discussions
- Site initiation training
- Early site visits following enrollment
- Routine site management
- Ongoing site communication and training
- Periodic site monitoring
- Review of the eCRF against source data for all subjects
- Data management quality control (QC) checks
- Statistical QC checks

16.2. Data Management

Based on the final eCRF, a database will be designed and built to meet US FDA: 21 Code of Federal Regulations (CFR) 11 requirements. A Data Management Plan will be written specifying the procedures that will be used for data cleaning, medical coding, SAE reconciliation, QC, laboratory data, and data cleaning that will occur for the study. A Data Validation Plan will be written and edit checks will be programmed and validated.

16.3. Monitoring

Monitoring visits will be conducted by representatives of the Sponsor according to the International Conference on Harmonisation (ICH) Guideline for GCP, and applicable regional regulations and guidelines.

A monitor (or monitors) will review and verify protocol compliance with a focus on AE/SAE reporting, eCRF data, source documentation, ICFs, and any other study-related documentation, including review of site pharmacy procedures, drug accountability documentation, and drug storage facilities and records.

Monitoring will be on an ongoing basis. Before database lock, 100% eCRF data verification will be performed against the source documents. The Investigator will agree to the monitor(s) making periodic site visits during the study. The monitor(s) and the study staff will agree upon the timing of these visits.

16.4. Confidentiality and Auditing

The Investigator, the Sponsor, and the Sponsor's representatives will preserve the confidentiality of all subjects participating in this study, in accordance with ICH GCP, local regulations, and institutional requirements. Only initials, date of birth, and study subject number will be used to

identify subjects on the eCRFs and other study-related documents submitted to the Sponsor (or designee). Documents that are not submitted to the Sponsor (eg, ICFs) should be kept in strict confidence by the investigative staff.

In compliance with ICH GCP, it is required that the Investigator and institution permit authorized representatives of the Sponsor, the IRB/IEC, the US FDA, and other appropriate regulatory authority or health authority inspectors direct access to all study-related sites, source data, documents, and reports for verification of study records and data. Direct access is the permission to examine, analyze, verify, and reproduce any records and reports that are important to the evaluation of a clinical study. The Investigator is obligated to inform and obtain consent from the subject to permit these representatives to have access to their study-related records for this verification. Any party (eg, domestic and foreign regulatory authorities, Sponsors, and auditors) with direct access should take all reasonable precautions within the constraints of the applicable regulatory requirement(s) to maintain the confidentiality of subjects.

16.5. Case Report Forms

eCRFs will be used for this study. Site personnel will receive training on eCRF completion. Each eCRF is to be reviewed and approved by the Investigator.

During periodic monitoring visits, the Investigator will make the eCRFs available to the study monitor so that he or she may verify the data entries with the source documentation.

16.6. Source Documents

The Investigator will prepare and maintain adequate and accurate source documents (eg, medical records, 12-lead ECG results, and raw data collection forms) to record all observations and other pertinent data for each subject enrolled into the study. The data recorded on the eCRFs will be derived from these source documents. The Investigator will ensure that data on the eCRFs and completed queries are accurate, consistent with source documentation, and submitted to the Sponsor in a timely manner. The Investigator will also ensure that all data on required study logs are accurate and kept up to date.

16.7. Records Retention

The Investigator must maintain essential study documents (protocol and amendments, completed eCRFs, source documentation, signed ICFs, relevant correspondence and approvals, and all other supporting documentation) until notified by the Sponsor. Subject identification codes (subject names and corresponding study numbers) will be retained for this same period and stored separately. Custody of the records may be transferred to another responsible party, acceptable to the Sponsor, which agrees to abide by the retention policies. Written notice of transfer must be submitted to the Sponsor. The Investigator must contact the Sponsor before disposing of any study records.

Records retention will follow the data protection requirements in each country.

16.8. Informed Consent

Written informed consent will be obtained from each subject before any study-related procedures are performed. The Investigator has an ethical and legal responsibility to ensure each subject

being considered for inclusion in the study is given a full explanation of the study. The Investigator, or his/her designee, shall inform each subject, in writing, of all aspects pertaining to participation in the study, including (but not limited to) aims, methods, anticipated benefits, and potential risks. Subjects will have the opportunity to inquire about details of the study and to decide whether to participate. Subjects should understand that they are free to refuse to participate in, or to withdraw from, the study at any time without prejudice or loss of medical care to which they are otherwise entitled. Each subject must personally sign and date a study-specific ICF to be a subject in the study. The ICF must be countersigned by the site Investigator (or designee) who conducted the informed consent discussion. This will be documented on a written ICF. Each ICF will include the elements required by US 21 CFR 50 and ICH E6, Section 4.8. The Investigator agrees to obtain approval from the Sponsor of any written informed consent for use in the study before submission to the IRB/IEC.

Each subject who provides written informed consent for the study (by signing and dating the ICF), will be given a copy of the signed ICF. The original will be kept in the subject's medical record or study chart as permitted by the institution. The Investigator will inform subjects of new information that may be relevant to the subjects' willingness to continue participation in the study according to local ethics requirements.

It is important to obtain complete follow-up for all subjects. Every attempt should be made to undertake all protocol-specified assessments and complete the eCRFs except for those subjects who specifically withdraw consent for release of such information.

Subjects will be provided a separate consent form before providing blood samples for genetic analysis and must be willing and able to provide consent as described above.

